10.0 Statistical Methods

The full statistical methods are detailed separately in the Statistical Analysis Plan.

The primary analysis model will be the semiparametric proportional odds (PO) ordinal logistic regression model¹⁶ for continuous outcome variables¹⁷. The PO model does not make any distributional assumption for the response variable, is robust to extreme values, and is invariant to transformations of the response variable. It is also extremely efficient when compared to linear regression if normality holds. The Wilcoxon nonparametric two-sample test is a special case of the PO model, but the PO model allows for baseline covariate adjustment. Note that we use covariate adjustment instead of change from baseline so as to not assume that (1) the baseline variable is linearly related to the response variable and (2) the slope of the baseline variable is 1.0.

For binary outcomes we will use the special case of the PO model that is the binary logistic regression model.

For safety analysis of clinical lab variables we use the most powerful and least arbitrary continuous variable analyses and include the empirical cumulative distribution function of post-randomization values of these variables. These continuous analyses will also provide estimates of incidence of such outcomes as hyper- and hypo-kalemia, but will be more sensitive than using only binary responses.

Trial	Experimental agent	Mean decrease in weight (kg) Experimental, (%)	Mean decrease in weight Control, (%)	Within group SD in Experimental Group (kg)
TRUE-AHF ⁸	Ularitide			
RELAX-AHF ¹⁸	Serelaxin	3.6	3.0	4.4
ASCEND-HF ⁹	Nesirtide			
EVEREST ¹⁹	Tolvaptan	3.3	2.7	3.3
TACTICS ²⁰	Tolvaptan	3.7	2.5	4.4
Secrets of HF ²¹	Tolvaptan	3.5	2.4	2.0
ROSE-HF ²²	Nesiritide	3.25	3.5	0.9
ROSE-HF ²²	Dopamine	3.4	3.5	0.9
MEAN		3.5	2.9	2.7

Changes in body weight from admission to discharge in previous literature

Changes in weight by IV 40mg Furosemide Equivalents (FE)

Trial	Experimental agent	Duration (days)	Daily IV loop diuretic dose in FE, mean or median (IQR)*	Median (IQR) decrease in weight (kg)/40mg IV FE	Difference associated with adverse HF outcomes
RELAX-AHF ²³	Serelaxin	5	80	0.42 (1.00, 0.14)	Below median value
DIUR-HF ¹⁴	None	3-5	137 (100, 200)	0.20 (0.281, 0.082)	Below median value
ASCEND-HF ²⁴	Nesiritide	2		0.42 (1.0, 0.05)	Below median value
PROTECT ²⁵	Rolofylline	4	80 (47, 133)	0.38 (0.8, 0.13)	Below median value
EVEREST ^{19,26}	Tolvaptan	4	80	0.30 (0.79, 0.03)	Below median value

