 - a. Repeated as per doubling of the cumulative Day 2 loop diuretic dose (log2 cumulative loop diuretic dose centered at 40mg)
- d) Spot urine sodium-based diuretic efficiency defined as the spot urine sodium concentration (mmol/L) on Day 2 per 40mg of IV furosemide equivalents (preceding loop diuretic dose)
- e) Fractional excretion of sodium (FENa)-based diuretic efficiency on Day 2 of IV therapy defined as the FENa from a spot urine test on Day 2 of IV therapy collected ~2 hours after bolus loop dose per 40 mg of IV furosemide equivalents.
 - a. Repeat as per doubling of the cumulative loop diuretic dose (log2 cumulative loop diuretic dose centered at 40mg)
- f) Urinary Na/K ratio at Day 2 of IV therapy adjusted for baseline.
- g) Calculated 6-hour sodium output on Day 2 of IV therapy using spot urine sodium collected 2 hours after bolus loop dose.
- h) Length of hospital stay, measured as days from admission to discharge
- i) Presence of symptoms of congestion and dyspnea at discharge, measured via blinded-physician exam and patient reported congestion scores.
- j) Hospital readmission within 30 days of discharge for any cause.
- k) Number of days at home without hospitalization or emergency room visit during 30-day follow up period.
- 1) Mean serum glucose during therapy
- m) Amount of total daily insulin doses (units) utilized per day during therapy, compared between treatment arms and to a "prior to enrollment" outpatient insulin regimen.
- n) Analyze the change in basic metabolic panel laboratory values and hemoglobin from baseline to end of study
- o) Serum potassium covariate with attention to both elevation and depression.

Hypokalemia levels are defined as

- a. Not hypokalemic: serum potassium > 3.4 mEq/L
- b. Mild: serum potassium 3.0 3.4 mEq/L
- c. Mod-Severe: serum potassium < 3.0 mEq/L

Hyperkalemia levels are defined as

- a. Not hyperkalemic: serum potassium < 5.1 mEq/L
- b. Mild: serum potassium 5.1 5.5 mEq/L
- c. Severe: serum potassium > 5.5 mEq/L

Safety Endpoints: Comparing differences among the two arms in the following:

- a) Estimated Glomerular Filtration Rate by the MDRD equation at discharge adjusted for baseline. A sensitivity analysis of eGFR by the CKD-EPI equation will also be done.
- b) Incidence of ketoacidosis as adjudicated by the CEC
- c) Serum glucose with attention to both elevation and depression.
 - a. Hypoglycemia is defined as:
 - i. Not hypoglycemic: serum glucose > 70 mg/dl

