 - ii. Mild: serum glucose 54-69 mg/dl
 - iii. Mod-Severe: serum glucose < 54 mg/dl
 - b. Hyperglycemia is defined as:
 - a. Not hyperglycemic: serum glucose < 200 mg/dl
 - b. Mild: serum glucose 200-300 mg/dl
 - c. Severe: serum glucose > 300 mg/dl
- d) Incidence of hypovolemic hypotension, defined as symptomatic hypotension with a sustained systolic blood pressure less than 90 mmHg lasting at least 30 minutes requiring fluid administration.
- e) Inpatient mortality

Design Considerations

Randomization

Patients will be randomized in a 1:1 ratio to receive either intervention or structured usual care. Randomization will use block randomization stratified by site with block sizes of 4.

Power and Sample Size

We anticipate dapagliflozin will increase the weight loss while decreasing the cumulative furosemide dose required to achieve euvolemia. On the basis of the historical literature, we project an increase in diuretic efficiency by 0.1kg/40mg IV furosemide in the Dapagliflozin arm to be a clinically meaningful difference. We project that our diuretic protocol will decrease variations in loop diuretic dosing, which drive large standard deviations. We project a normally distributed standard deviation within each arm to be 0.25kg/40mg. A sample size of 120 experimental subjects and 120 control subjects will have 87% power to detect a probability of 0.611 that an observation in the Dapagliflozin arm is less than an observation in the structured usual care arm using a Wilcoxon (Mann-Whitney) rank-sum test with a 0.05 two-sided significance level.

Statistical Approach

Descriptive Analysis

Initially, we will describe the study cohort pooled across all sites, both overall and grouped by treatment assignment. To characterize the study sample, demographic, clinical, and lab data will be described overall and by treatment arm. Categorical variables will be described using frequencies and proportions; continuous variables will be described using means and standard deviations as well as medians and interquartile ranges (IQR). Missingness will be recorded for each variable. To further assess the distribution of variables, graphical summaries will be displayed using graphs such as box-plots, dot-plots,

violin-plots, and/or histograms. No statistical testing will be done to compare characteristics across groups. At a minimum, the following baseline variables will be described:

- Age (years)
- Sex

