- h) The association of length of hospital stay with treatment assignment will be analyzed using the Wilcoxon Rank Sum test

- The association of presence of symptoms of congestion and dyspnea at discharge measured via blinded physician exam and patient reported congestion scores with treatment assignment will be analyzed using the Pearson chi-square test. A proportional odds model will be used to assess the association of discharge congestion score with treatment assignment, adjusting for baseline congestion.
- j) Cumulative incidence of all cause hospital readmission within 30 days of index hospitalization discharge will be graphed by treatment arm treating death as a competing risk. The association of all cause hospital readmission within 30 days of index hospitalization discharge with treatment assignment will be analyzed using the Pearson chi-square test.
- k) The association of number of days at home without hospitalization or emergency room visit during the 30-day follow-up period with treatment assignment will be analyzed using the Wilcoxon Rank Sum test. For purposes of analysis, subjects who died within 30 days of the index hospital discharge will be assigned a value of 0 days at home
- 1) The association of mean serum glucose during therapy with treatment assignment will be analyzed using the Wilcoxon Rank Sum test
- m) Total daily insulin doses (units) utilized per day during therapy will be compared between treatment arms in all comers and in those with diabetes at baseline using a Wilcoxon Rank Sum Test. Total daily insulin doses utilized per day during therapy will be compared to a 'prior to enrollment' utilization using the Wilcoxon Signed Rank Test.
- n) The change in basic metabolic panel laboratory values and hemoglobin from baseline to the end of study will be compared across treatment groups using the Wilcoxon Rank Sum test.
- o) Serum potassium trends over time by treatment assignment will be graphed. Descriptive statistics
 of the daily raw potassium values and kalemic status during hospitalization by treatment group
 will be reported and compared across treatment assignments by Wilcoxon Rank Sum tests and
 Pearson's chi-square tests, respectively.

Safety Analyses:

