All multivariable models will adjust for the same key covariates as specified for the primary outcome, as sample size permits. Appropriate model diagnostics will be run to assess model fit. If model diagnostics suggest the planned approach violates necessary assumptions, alternative methods will be pursued.

- a) The association of estimated Glomerular Filtration Rate (eGFR) at discharge, calculated using the MDRD equation, with treatment assignment will be modeled using covariate-adjusted PO regression, adjusting for baseline eGFR. The analysis will be repeated calculating eGFR using the CKD-EPI equation as well.
- b) The association of the incidence of ketoacidosis as adjudicated by the CEC with treatment assignment will be analyzed using the Pearson chi-square test.
- c) Serum glucose trends over time by treatment assignment will be graphed. Descriptive statistics of the daily raw glucose values and the glycemic status during hospitalization by treatment group will be reported and compared across treatment assignment by Wilcoxon Rank Sum tests and Pearson's chi-square tests, respectively.
- d) The association of incidence of hypovolemic hypotension, defined previously, with treatment assignment will be analyzed using the Pearson chi-square test.

e) The association of inpatient mortality with treatment assignment will be analyzed using the Pearson chi-square test and univariate logistic regression.

Sensitivity Analyses:

Our sensitivity analysis will be a covariate-adjusted proportional odds (PO) regression model with our outcome being log-transformed weight at the minimum of Day 5 or discharge and the main predictor being treatment assignment. Adjusting covariates will be as defined in the primary analysis. Appropriate model diagnostics will be run to assess model fit. If model diagnostics suggest the planned approach violates necessary assumptions, alternative methods will be pursued.

Heterogenicity of Treatment Effect:

Heterogenicity of Treatment Effect (HTE) will be assessed refitting the primary model with the covariate of interest interacted with treatment assignment. The HTE analysis will include the following variables:

- Sex (male or female)
- Baseline edema score (No-Mild/Moderate/Severe)
- Baseline NTproBNP
 - Continuous
 - Dichotomize by median NTproBNP [above/below]
- Baseline BMI-adjusted BNP: defined as a 4% increase in NT-proBNP for every 1 unit increase in baseline BMI above a BMI of 20kg/m²
 - Continuous

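### Potassium and glucose status is tested by a chi-square that ignores the order of its levels, and raw values by an unadjusted rank test, where the protocol promises baseline-adjusted continuous analysis with distribution plots

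*SAP*

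**What the plan says.** The SAP's Exploratory Endpoints o) and Safety Endpoints c) divide potassium and glucose, in each direction, into three ordered levels: none, mild, and a top level such as "Mod-Severe: serum potassium < 3.0 mEq/L". Two comparisons follow for each analyte. For potassium, Exploratory Analyses o) takes descriptive statistics "of the daily raw potassium values and kalemic status during hospitalization by treatment group" and tests the raw values by Wilcoxon and the status by Pearson chi-square. Safety Analyses c) does the same for glucose: values and status are "compared across treatment assignment by Wilcoxon Rank Sum tests and Pearson's chi-square tests, respectively". Trend graphs are planned. Neither item names a baseline covariate or an empirical distribution plot, and neither says which of a patient's daily values sets the status.

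The protocol describes something different. Section 10.0 commits laboratory safety variables to continuous analysis with the empirical cumulative distribution. Incidences such as hypo- and hyperkalemia are to be read from that analysis, which "will be more sensitive than using only binary responses". Sections 2.3 (potassium) and 2.4 (glucose) both ask for adjustment for the baseline value.

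**The concern.** Pearson's test on a 2 x 3 table has 2 degrees of freedom and gives the same answer if the three levels are shuffled. It therefore uses neither the order of the levels nor the distance between values within a level. The Wilcoxon test beside it does use the values, but without the baseline covariate, and a comparison of typical daily values is not aimed at each patient's low or high extreme.

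The SAP uses the protocol's method elsewhere: baseline-adjusted proportional odds regression for NT-proBNP, eGFR and the ordered discharge congestion score. It gives no reason for leaving it here. Protocol 2.1 says that establishing safety would make the trial worthwhile even if the primary endpoint fails, so a laboratory comparison that too readily shows no difference has a cost.

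**Working it through.** **The plan's own power figure.** The only one is for the primary endpoint: "A sample size of 120 experimental subjects and 120 control subjects will have 87% power" with a "rank-sum test with a 0.05 two-sided significance level". Its inputs are a difference of 0.1 and an SD of 0.25 kg per 40 mg, so d = 0.1/0.25 = 0.4.

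- P(X<Y) = Φ(0.1/(0.25·√2)) = Φ(0.283) = 0.611, as stated.
- Power = Φ(0.4·√(120/2) − 1.96) = Φ(3.098 − 1.96) = 87%.
- With the Wilcoxon efficiency 3/π: Φ(3.098·√0.955 − 1.96) = Φ(1.07) = 86%. Simulation gives 85%.

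The figure reproduces. It also shows what a full-scale rank test can do at a 0.4 SD difference. Nothing in the documents says that potassium or glucose would differ by 0.4 SD; it is used below only as a common yardstick.

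**Assumptions for potassium** (none is in the documents). Each patient's lowest value is normal, control mean 3.5, 3.7 or 3.9 mEq/L, SD 0.4 or 0.5. The treated arm is lower by 0.4 SD. Cuts are at 3.0 and 3.45 (the SAP's 3.0 and 3.4 with values reported to one decimal). There are 120 patients per arm, and two-sided 0.05 is carried over from the primary endpoint because no level is stated for these tests.

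**One setting by hand: mean 3.7, SD 0.5, shift −0.2.**

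| Level | Control | Treated |
|---|---|---|
| < 3.0 | Φ(−1.40) = 0.081 | Φ(−1.00) = 0.159 |
| mild | Φ(−0.50) − 0.081 = 0.228 | Φ(−0.10) − 0.159 = 0.301 |
| none | 0.691 | 0.540 |

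The half-differences are 0.039, 0.0365 and 0.0755, and the level averages are 0.120, 0.2645 and 0.6155. The Pearson noncentrality is 240·(0.039²/0.120 + 0.0365²/0.2645 + 0.0755²/0.6155) ≈ 6.5. On 2 df that is about 62% power, which the simulation matches. In the same setting an ordered test of the levels has 71%, the rank test of the values 85%, and a baseline-adjusted rank analysis 96%.

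**Power across the potassium settings, shift toward more hypokalemia**

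| Test | Power |
|---|---|
| Pearson, three levels | about 45-69% |
| Ordered test, same levels | about 56-78% |
| Rank test of lowest value | about 85% |

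Ignoring the order costs about 9-11 points (78 − 69 and 56 − 45). Cutting the scale and ignoring the order together cost about 16-40 points (85 − 69 and 85 − 45).

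**Glucose** (assumed mean 150, SD 55 mg/dl, shift −20, one value per patient): Pearson has 29% for hypoglycemia and 39% for hyperglycemia, the ordered test 38% and 44%, and the rank test of the values 79%.

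**Baseline adjustment.** With an assumed correlation of 0.6, and rank ANCOVA standing in for the proportional odds model, power rises from 79% to 91% for glucose and from 85-86% to 96% for potassium shifted by −0.2. The gain is roughly 10-12 points.

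**Tail-only effect.** Let 8% of treated patients fall below 3.0 and leave the rest unchanged. Across the same potassium settings Pearson has about 19-75% power, the ordered test 17-38%, and the rank test of the lowest value 14-19%. The ranking reverses.

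**Repeated values.** Protocol 5.0 requires at least one metabolic panel a day, and the SAP does not say how the days are combined. If 2-5 days per patient were pooled as independent, the Wilcoxon type I error would be 14%, 21% and 24% at within-patient correlations of 0.3, 0.5 and 0.7. The SAP does not say that it would pool them; day-by-day tests are an equally possible reading. One value per patient removes the question.

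**The case against.** The strongest reply is that the plan already tests the continuous values. The Wilcoxon half of the quoted sentence applies to the daily raw values. Exploratory l) tests mean glucose, and n) tests change from baseline in the metabolic panel. A reader might infer that the underlying values are ignored; the documents do not support that. Nor does the SAP contradict Protocol 10.0 outright: that sentence warns against relying only on binary responses, and the SAP uses three levels alongside continuous tests. What stands against the plan is narrower. The baseline covariate and the distribution plots are missing, and item n) does not supply the first, because Protocol 10.0 itself prefers covariate adjustment to change scores.

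A second reply is that a location test and a category test complement each other. That is right. With wider spread between patients and no shift (potassium SD × 1.4), the raw-value Wilcoxon has 6% power, against 45% (hypokalemia) and 36% (hyperkalemia) for Pearson. The tail-only result above points the same way. A reader might infer that the chi-square always has far less power, or that the category comparison should be dropped; neither follows. Per-patient extremes do recover part of what a location test misses. With larger day-to-day swings within patients (× 1.4) and no shift, rank tests of the lowest and highest value have 36-38%, Pearson 27-34%, and a Wilcoxon test of patient means 4%.

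Third, direction matters. The same 0.4 SD shift toward higher potassium gives Pearson only about 32-63%, but that is a missed benefit on hypokalemia, not a missed harm, and should not be quoted as the loss.

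Finally, the stakes are limited. Potassium is exploratory in both documents. Hypoglycemia that may prolong the stay is also adjudicated by the events committee and collected as an adverse event.

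**Conclusion.** The point holds in a limited form. For potassium and glucose the SAP leaves out the baseline adjustment and empirical distributions that the protocol promises, and it tests ordered status with a test that ignores order. Under a shift of the whole distribution, the order alone is worth about 9-11 points of power in the potassium settings, the full scale considerably more, and baseline adjustment roughly 10-12 points on top of an unadjusted rank test. Under an effect confined to a few patients, the planned chi-square is the better test.

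The departure from the protocol can be read directly from the texts. Every power figure for the laboratory values rests on assumed means, SDs, shifts, tail fractions and correlations. This is an inexpensive improvement to one safety endpoint and one exploratory endpoint; it does not affect the primary analysis.

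**What to change.** In SAP Exploratory Analyses o) and Safety Analyses c):

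- Make the main comparison a proportional odds model of each patient's lowest and, separately, highest post-randomization value, for potassium and glucose in turn, adjusted for the baseline value.
- From each model report, by arm, the probability of crossing each stated cut-off, beside the empirical distribution plots.
- Keep the three-level incidence tables, with arm differences and confidence intervals, so that a tail-only effect stays visible. If status is modelled, use its order.
- State which value sets a patient's status.
- Reconcile the cut-offs first: the SAP's top glucose level is > 300 mg/dl where Protocol 2.4 names > 400, and a glucose of exactly 70 falls in no SAP hypoglycemia level.

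The cost is SAP wording and a little code, with no new data. The downside is that an extreme depends on how many samples were drawn, and stays differ in length, so the number of laboratory days by arm should be shown beside the result.

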Efficacy and Safety of Dapagliflozin in Acute Heart Failure

DICTATE-AHF

NCT 04298229

Statistical Analysis Plan

Version	Approval	Summary of Changes
Number/Amendment	Date	
1.0/ Original protocol	10.2021	Not applicable
2.0/Amendment One	3.2023	 Modified text to include patients without diabetes Sensitivity endpoint analysis - changed diuretic dose analyses to be centered on 40mg IV furosemide from 20mg Defined serum potassium values to define severity categories of hypokalemia Defined serum glucose values to define severity categories of hypoglycemia and subsequent analyses changes for these new categories Added eGFR calculation to also be done with the CKD-EPI calculation Primary Analysis: changed the covariates to only be baseline weight (removing other covariates) Exploratory Outcome: Altered analysis of 30-day readmission to include death as a competing risk Exploratory Outcome: clarified total daily insulin doses will be compared between treatment arms and prior to enrollment Exploratory Outcome: Added 24-hour and spot urine sodium measures Added Heterogenicity of Treatment Effect analyses Added changes in serum chemistries by treatment arm

Introduction

This document describes the statistical analysis plan (SAP) for a randomized, open-label, multi-center trial studying the sodium-glucose cotransporter-2 inhibitor (SGLT2), Dapagliflozin, in patients with or without Type II diabetes (T2DM) admitted with acute decompensated heart failure (ADHF).

Patients with ADHF are typically admitted to the hospital due to symptoms of congestion with loop diuretics being the primary mode of treatment; however, loop diuretics are not always sufficient in helping patients achieve adequate decongestion.^{1,2,3} In fact, congestion remains the major cause of hospital readmission for heart failure. In addition, an increasing percentage of patients admitted with ADHF also have T2DM. It has been shown that SGLT2-inhibitors, approved for anti-hyperglycemic therapies, also have diuretic and natriuretic effects.⁴ The acute diuretic effects in a population with ADHF, with or without concomitant hyperglycemia, undergoing intravenous diuresis are currently unknown. This trial hypothesizes patients randomized to receive dapagliflozin will have improved decongestion when compared to those receiving structured usual care.

Treatment arms

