Patients with or without T2DM hospitalized with ADHF will be randomized within 24 hours of evaluation of ADHF in 1:1 ratio to either intervention or structured usual care defined as follows:

- a) **Intervention:** Previous diabetic therapies will be discontinued, and patients will receive protocolized diuretic therapy plus the addition of open label SGLT2 inhibitor therapy with dapagliflozin 10 mg orally once daily for the duration of the study the minimum of 5 days or hospital discharge.
- b) **Structured usual care:** Previous diabetic therapies will be discontinued, and patients will receive protocolized diuretic therapy.

Endpoints

Primary Endpoint:

The primary endpoint is to determine the cumulative change in weight (kg) per 40mg of IV furosemide equivalents from enrollment to the minimum of Day 5 or discharge between 1) protocolized diuretic therapy (structured usual care) and 2) dapagliflozin plus protocolized diuretic therapy guided by urine output.

Sensitivity Endpoint:

The cumulative change in weight (kg) per doubling of the cumulative loop diuretic (analyzed as log2 of the cumulative loop diuretic dose centered on 40mg of IV furosemide equivalent and winsorized at 40mg) from enrollment to Day 5 or discharge between 1) structured usual care and 2) dapagliflozin plus structured usual care

Secondary Endpoints: Comparing differences among the two arms in the following:

a) Incidence of worsening heart failure during hospitalization requiring i) IV inotropic therapy, ii) new admission to an intensive care unit (ICU), iii) new non-invasive positive pressure ventilation with bi-level positive airway pressure, or iv) increase in the IV diuretic protocol intensity by 2 rows after Study Day 1 as adjudicated by the Clinical Event Committee (CEC).

b) Hospital readmission within 30 days of discharge for ADHF or diabetic reasons as adjudicated by the CEC.

Exploratory Endpoints: Comparing differences among the two arms in the following:

- a) NT-proBNP at baseline to discharge adjusted for baseline.
- b) Urine-output based diuretic efficiency defined as the Day 2 24-hour total urine output (ml) per 40/mg of IV furosemide equivalents
 - a. Repeated as per doubling of the cumulative loop diuretic dose (log2 cumulative loop diuretic dose centered at 40mg)
- c) Urine sodium-based diuretic efficiency defined as the Day 2 24-hour total urine sodium excretion (mmol) per 40mg of IV furosemide equivalents (total loop diuretic dose over Day 2)

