Inpatient and 30-day endpoints of interest will be summarized overall and by treatment assignment. Categorical variables will be described using frequencies and proportions; continuous variables will be described using means and standard deviations as well as medians and interquartile ranges (IQR). Missingness will be recorded for each variable. For those endpoints that are a composite of multiple endpoints, such as incidence of worsening heart failure (requiring IV inotropic therapy, new admission to an ICU, new non-invasive positive pressure ventilation with bi-level positive airway pressure, or increase in the IV diuretic protocol intensity by 2 rows after Day 1 as adjudicated by the CEC) and hospital readmission within 30 days of index hospitalization discharge (for heart failure-related reasons or diabetic reasons), frequencies will be summarized overall and for each level.

No statistical testing will be done to compare characteristics across groups.

Main Analysis

All model results (unadjusted and adjusted) will be summarized with point estimates, 95% confidence intervals (CIs), and p-values displayed in tabular form or graphically, along with appropriate model fit statistics. Missingness in adjusting covariates will be addressed using multiple imputation based on predictive mean matching.

Primary Analysis: Our main analysis will be a covariate-adjusted proportional odds (PO) regression model with our outcome being cumulative change in weight per 40mg of IV furosemide equivalents from

enrollment to the minimum of Day 5 or discharge and the main predictor being treatment assignment. Adjusting covariates will be pre-specified and include baseline weight. Baseline weight will be fit with restricted cubic splines with 3 knots to relax the linearity assumptions.

Secondary Analyses:

Appropriate model diagnostics will be run to assess model fit. If model diagnostics suggest the planned approach violates necessary assumptions, alternative methods will be pursued.

- a) Binary logistic regression will be used to assess the association of the incidence of worsening heart failure as adjudicated by the CEC with treatment assignment.

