- b) A time to event analysis is proposed to assess the association of 30-day hospital readmission for ADHF or diabetes-related reasons. Cumulative incidence of hospital readmission for heart failure or diabetes-related reasons will be graphed by treatment arm death as a competing risk. Multivariable Cox proportional hazards models stratified by enrollment site will be fit to assess the association of time to hospital readmission for reasons of interest with treatment assignment.

Exploratory Analyses:

Appropriate model diagnostics will be run to assess model fit. If model diagnostics suggest the planned approach violates necessary assumptions, alternative methods will be pursued.

- a) The association of NT-proBNP at discharge with treatment arm will be modeled using covariateadjusted PO regression, adjusting for NT-proBNP at baseline (Day 1).
- b) The association of Day 2 24-hour total urine output per the following methods in which diuretic dose is centered at 40mg and values less than 40mg are winsorized to 40mg:
 - a. 40 mg of IV furosemide equivalents will be analyzed using the Wilcoxon Rank Sum test
 - b. Doubling of the loop diuretic dose to account for the logarithmic dose-response curve will be analyzed using the Wilcoxon Rank Sum test.
- c) Urine sodium-based diuretic efficiency defined as the Day 2 24-hour total urine sodium excretion (mmol) per 40mg of IV furosemide equivalents (total loop diuretic dose over Day 2) will be analyzed using the Wilcoxon Rank Sum test.
 - a. Repeated as per doubling of the cumulative Day 2 loop diuretic dose (log2 cumulative loop diuretic dose centered at 40mg) will be analyzed using the Wilcoxon Rank Sum test.
- d) Spot urine sodium-based diuretic efficiency defined as the spot urine sodium concentration (mmol/L) on Day 2 per 40mg of IV furosemide equivalents (preceding loop diuretic dose) will be analyzed using the Wilcoxon Rank Sum test.
- e) The association of Day 2 fractional excretion of sodium (FENa)-based diuretic efficiency determined from spot urine collected 2 hours after bolus loop dose with treatment arm will be analyzed using the Wilcoxon Rank Sum test.
- f) The association of Day 2 urinary Na/K ratio with treatment arm will be analyzed using covariateadjusted PO regression, adjusting for baseline (Day 1) urinary Na/K ratio.
- g) The association of calculated Day 2 6-hour sodium output with treatment assignment will be analyzed using the Wilcoxon Rank Sum test

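### The sensitivity analysis of the primary endpoint models final weight with no loop diuretic dose term, so the SAP's stated sensitivity endpoint (weight change per doubling of dose) has no specified model

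*SAP*

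**What the plan says.** Three parts of the current SAP bear on this.

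- **Endpoints, Sensitivity Endpoint.** The quantity is "The cumulative change in weight (kg) per doubling of the cumulative loop diuretic", with dose "analyzed as log2 of the cumulative loop diuretic dose centered on 40mg of IV furosemide equivalent and winsorized at 40mg", from enrolment to Day 5 or discharge, compared between arms.
- **Sensitivity Analyses.** The model is proportional odds with "outcome being log-transformed weight at the minimum of Day 5 or discharge and the main predictor being treatment assignment". Covariates are those of the primary analysis.
- **Main Analysis, Primary Analysis.** The outcome is weight change per 40 mg of IV furosemide equivalents. On covariates: "Adjusting covariates will be pre-specified and include baseline weight". Baseline weight enters as a 3-knot restricted cubic spline. No other covariate is named.

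Protocol 10.0 says that the proportional odds model "is robust to extreme values, and is invariant to transformations of the response variable". It also says that the trial uses covariate adjustment rather than change from baseline.

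Per-doubling tests are specified under Exploratory Analyses (b) and (c), but only for Day 2 urine output and Day 2 urine sodium.

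**The concern.** The primary endpoint divides weight change by dose on a linear scale. Exploratory Analyses (b) itself cites a logarithmic dose-response curve as the reason for per-doubling versions. The Power and Sample Size section expects dapagliflozin to lower the cumulative furosemide dose. An arm difference in the primary endpoint could therefore come partly or wholly from dose, and its size would depend on how dose is scaled. The sensitivity endpoint is the natural check on that, yet the section that should analyse it contains no dose.

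An analyst who follows the SAP exactly would never test the primary result on a log-dose scale. An analyst who notices the gap would have to choose a ratio, a covariate or weight alone, possibly after seeing results by arm.

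**Working it through.** **1. The plan's own figure.** The point does not rest on the power statement, but it was checked.
- P = Φ(0.1 / (0.25 × √2)) = 0.611, as stated.
- Normal approximation, 120 per arm: Φ(0.1 / (0.25 × √(2/120)) − 1.96) = Φ(3.10 − 1.96) = 87.3%, against the stated 87%. A simulated Wilcoxon test (20,000 runs) gives 85.3%.

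**2. Where dose appears.**

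| | Outcome | Dose in outcome | Dose as covariate |
|---|---|---|---|
| Primary Analysis | weight change per 40 mg | yes, linear | not named |
| Sensitivity Endpoint | weight change per doubling | yes, log2 | not stated |
| Sensitivity Analyses | log final weight | no | not named |

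**3. The log on weight.** Log is monotone and the model uses only the order of the responses. In a test fit, weight and log weight gave the same treatment log-odds ratio, -0.009 (SE 0.242).

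**4. The dose scale matters.** Take cumulative doses of 800 and 400 mg with the same weight loss.
- Linear denominators: 800/40 = 20 and 400/40 = 10, a factor of 2.
- Log2 denominators: log2(20) = 4.32 and log2(10) = 3.32, a factor of 4.32/3.32 = 1.30.

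Halving the dose raises the linear score by 100% but the log2 score by about 30%.

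**5. Response of each model to dose.** One simulated data set, n = 240. Weight loss had mean 3.5 kg and SD 2.7, the across-trial means in the weight table of Protocol 10.0. Assumed: median cumulative dose 560 mg (log-SD 0.6) and baseline weight mean 95 kg (SD 20). Baseline weight was fitted linearly and the response was grouped in 40 ordered categories. Final weights were held fixed and the dapagliflozin-arm dose was multiplied by a factor.

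| Dose factor | Log final weight | Loss per doubling | Loss per 40 mg |
|---|---|---|---|
| 1 | -0.009 | -0.29 | -0.31 |
| 0.7 | -0.009 | 0.03 | 0.26 |
| 0.5 | -0.009 | 0.39 | 0.78 |

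Entries are treatment log-odds ratios. For the two dose-based columns, higher means more loss per unit of dose on dapagliflozin. Single-data-set values have standard errors near 0.23 and are illustrative. What matters is that the first column cannot move.

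**6. If a ratio is meant.** The denominator log2(max(dose, 40)/40) is 0 at or below 40 mg, so the ratio is undefined there. It is also unstable just above: a 0.5 kg loss at 41 mg scores 0.5 / log2(41/40) = 0.5 / 0.0356 = 14.0, more than a 10 kg loss at 80 mg (10 / 1 = 10). With 1 + log2(max(dose, 40)/40), the scores are 0.5 / 1.0356 = 0.48 and 10 / 2 = 5.

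**7. Side note, Day 2 endpoints.**
- Urine output, Exploratory Analyses (b): "diuretic dose is centered at 40mg and values less than 40mg are winsorized to 40mg". The log2 term is 0 at or below 40 mg.
- Urine sodium, (c): "Repeated as per doubling of the cumulative Day 2 loop diuretic dose (log2 cumulative loop diuretic dose centered at 40mg", with no winsorizing stated. At 20 mg the term is log2(20/40) = −1, so 100 mmol would score −100 as a ratio, against +100 at 80 mg.
- FENa: Exploratory Endpoints (e) lists a per-doubling repeat, but Exploratory Analyses (e) gives no test for it.

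**The case against.** The best defence is that the final-weight model is sound in its own right. Protocol 10.0 prefers adjustment for baseline to change scores, so final weight adjusted for baseline weight is the protocol's own way to study weight change. That stands, and only the dose term is missing.

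The Description of Endpoints section also promises summaries by arm, so the sensitivity endpoint may still be described. What it lacks is a specified model. The clause allowing alternative methods does not fill the gap, because it applies only when diagnostics fail.

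Four stronger readings are tempting, and the documents do not support them.

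- *The SAP has only one sensitivity analysis.* It also labels the CKD-EPI repeat of eGFR as one. The final-weight model is the only one bearing on the primary endpoint.
- *The log was meant for dose and was put on weight by mistake.* This is plausible, since the log on weight does nothing, but no text shows it.
- *The sensitivity endpoint is an ill-defined ratio.* The SAP never says that it is a ratio. Centring also suits a regression covariate, which avoids a zero denominator.
- *The primary result is undermined.* Nothing in the primary model depends on this analysis, and no decision rule uses it.

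**Conclusion.** The contradiction is between two parts of the current SAP. It does not come from the version table, whose entry "changed diuretic dose analyses to be centered on 40mg IV furosemide from 20mg" shows only that the dose scaling was revisited. The stated sensitivity endpoint and the specified sensitivity analysis are different quantities, and the specified one is blind to dose.

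The consequence is limited. The primary analysis, sample size, power and alpha stand. What is lost is a pre-specified test of whether the primary finding depends on the linear per-40 mg scaling. This should be fixed, but it is a reconciliation of wording rather than a design fault.

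The conclusion rests on the text alone. The fitted figures rest on assumed doses and baseline weights and show direction only. They do not predict how far the trial's own result would move.

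**What to change.** Reconcile the Sensitivity Endpoint and Sensitivity Analyses sections before data are seen by arm.

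1. Make the per-doubling endpoint the outcome of the same proportional odds model as the primary, with baseline weight as covariate, and write out its formula.
2. If a ratio is used, choose and justify a denominator kept away from zero. One example is 1 + log2(max(dose, 40)/40). This equals log2(max(dose, 40)/20), so it must be reconciled with the 40 mg centring text. The version table gives the former 20 mg centre but not the floor used with it, so identity with the superseded definition cannot be assumed.
3. If log2 dose is entered as a covariate instead, say so, and state the limitation. Dose is post-randomization and titrated to urine output (Protocol 5.3.2), so the arm effect has a different meaning and can be biased.
4. Keep final weight adjusted for baseline weight, without the log, as a separately labelled weight-only analysis.
5. Apply the same dose formula and winsorizing to the Day 2 per-doubling endpoints for urine output and urine sodium. For FENa, add a test for the per-doubling repeat or delete it.

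The cost is SAP wording and a few lines of code, with no new data.
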